# N I H STROKE SCALE

Patient Identification \_\_\_\_\_

Pt. Date of Birth \_\_\_\_/\_\_\_\_/\_\_\_\_

Hospital \_\_\_\_\_ (\_\_\_\_-\_\_\_\_)

Date of Exam \_\_\_\_/\_\_\_\_/\_\_\_\_

Interval:  Baseline  2 hours post treatment  24 hours post onset of symptoms  $\pm$ 20 minutes  7-10 days  
 3 months  Other \_\_\_\_\_ (\_\_\_\_)

7. Limb Ataxia: This item is aimed at finding evidence of a unilateral cerebellar lesion. Test with eyes open. In case of visual defect, ensure testing is done in intact visual field. The finger-nose-finger and heel-shin tests are performed on both sides, and ataxia is scored only if present out of proportion to weakness. Ataxia is absent in the patient who cannot understand or is paralyzed. Only in the case of amputation or joint fusion, the examiner should record the score as untestable (UN), and clearly write the explanation for this choice. In case of blindness, test by having the patient touch nose from extended arm position.
	
0 - Absent.
 
1 - Present in one limb.
 
2 - Present in two limbs.
 
UN - Amputation or joint fusion, explain: _____
	
_____

8. Sensory: Sensation or grimace to pinprick when tested, or withdrawal from noxious stimulus in the obtunded or aphasic patient. Only sensory loss attributed to stroke is scored as abnormal and the examiner should test as many body areas (arms [not hands], legs, trunk, face) as needed to accurately check for hemisensory loss. A score of 2, "severe or total sensory loss," should only be given when a severe or total loss of sensation can be clearly demonstrated. Stuporous and aphasic patients will, therefore, probably score 1 or 0. The patient with brainstem stroke who has bilateral loss of sensation is scored 2. If the patient does not respond and is quadriplegic, score 2. Patients in a coma (item 1a-3) are automatically given a 2 on this item.
	
0 - Normal; no sensory loss.
 
1 - Mild-to-moderate sensory loss; patient feels pinprick is less sharp or is dull on the affected side; or there is a loss of superficial pain with pinprick, but patient is aware of being touched.
 
2 - Severe to total sensory loss; patient is not aware of being touched in the face, arm, and leg.
	
_____


9. Best Language: A great deal of information about comprehension will be obtained during the preceding sections of the examination. For this scale item, the patient is asked to describe what is happening in the attached picture, to name the items on the attached naming sheet and to read from the attached list of sentences. Comprehension is judged from responses here, as well as to all of the commands in the preceding general neurological exam. If visual loss interferes with the tests, ask the patient to identify objects placed in the hand, repeat, and produce speech. The intubated patient should be asked to write. The patient in a coma (item 1a-3) will automatically score 3 on this item. The examiner must choose a score for the patient with stupor or limited cooperation, but a score of 3 should be used only if the patient is mute and follows no one-step commands.
	
0 - No aphasia; normal.
 
1 - Mild-to-moderate aphasia; some obvious loss of fluency or facility of comprehension, without significant limitation on ideas expressed or form of expression. Reduction of speech and/or comprehension, however, makes conversation about provided materials difficult or impossible. For example, in conversation about provided materials, examiner can identify picture or naming card content from patient's response.
 
2 - Severe aphasia; all communication is through fragmentary expression; great need for inference, questioning, and guessing by the listener. Range of information that can be exchanged is limited; listener carries burden of communication. Examiner cannot identify materials provided from patient response.
 
3 - Mute, global aphasia; no usable speech or auditory comprehension.
	
_____


10. Dysarthria: If patient is thought to be normal, an adequate sample of speech must be obtained by asking patient to read or repeat words from the attached list. If the patient has severe aphasia, the clarity of articulation of spontaneous speech can be rated. Only if the patient is intubated or has other physical barriers to producing speech, the examiner should record the score as untestable (UN), and clearly write an explanation for this choice. Do not tell the patient why he or she is being tested.
	
0 - Normal.
 
1 - Mild-to-moderate dysarthria; patient slurs at least some words and, at worst, can be understood with some difficulty.
 
2 - Severe dysarthria; patient's speech is so slurred as to be unintelligible in the absence of or out of proportion to any dysphasia, or is mute/anarthric.
 
UN - Intubated or other physical barrier, explain: _____
	
_____

# N I H STROKE SCALE

Patient Identification \_\_\_\_\_

Pt. Date of Birth \_\_\_\_/\_\_\_\_/\_\_\_\_

[figure not shown]
Hospital \_\_\_\_\_ (\_\_\_\_-\_\_\_\_)

Date of Exam \_\_\_\_/\_\_\_\_/\_\_\_\_

Interval:  Baseline  2 hours post treatment  24 hours post onset of symptoms  $\pm$ 20 minutes  7-10 days  
 3 months  Other \_\_\_\_\_(\_\_\_\_)

11. Extinction and inattention (formerly Neglect): Sufficient information to identify neglect may be obtained during the prior testing. If the patient has a severe visual loss preventing visual double simultaneous stimulation, and the cutaneous stimuli are normal, the score is normal. If the patient has aphasia but does appear to attend to both sides, the score is normal. The presence of visual spatial neglect or anosagnosia may also be taken as evidence of abnormality. Since the abnormality is scored only if present, the item is never untestable.
	
0 - No abnormality.
 
1 - Visual, tactile, auditory, spatial, or personal inattention or extinction to bilateral simultaneous stimulation in one of the sensory modalities.
 
2 - Profound hemi-inattention or extinction to more than one modality; does not recognize own hand or orients to only one side of space.
	
_____

---	--	--------------

**You know how.**

[figure not shown]
**Down to earth.**

**I got home from work.**

**Near the table in the dining  
room.**

**They heard him speak on the  
radio last night.**

**MAMA  
TIP – TOP  
FIFTY – FIFTY  
THANKS  
HUCKLEBERRY  
BASEBALL PLAYER**

[Redacted]

[Redacted]

[Redacted]

[Redacted]

[Redacted]

[Redacted]

[Redacted]

[Redacted]

[Redacted]

[Redacted]

[Redacted]

[Redacted]

[Redacted text block]

[Redacted text block]

[Redacted text block]

[Redacted text block]

[Redacted text block]

[Redacted text block]

[Redacted text block]

[Redacted text block]

[Redacted text block]

[Redacted text block]

---

[Redacted text block]

[REDACTED]

[REDACTED]

[REDACTED]

[REDACTED]

[REDACTED]

[REDACTED]

[REDACTED]

[REDACTED]

[REDACTED]

[REDACTED]

[REDACTED]

[REDACTED]

[REDACTED]

[REDACTED]

[REDACTED]

[REDACTED]

[Redacted]

[Redacted]

[Redacted]

[Redacted]

[Redacted]

[Redacted]

[Redacted]

[Redacted]

[Redacted]

[Redacted]

[Redacted]

[Redacted]

[Redacted]

[REDACTED]

[REDACTED]

[REDACTED]

## Appendix W: Portico IDE FlexNav Study Synopsis

### 1. PURPOSE

#### 1.1 Indications for Use

The Portico™ valve is indicated for transcatheter delivery in patients with symptomatic severe native aortic stenosis who are considered high or extreme surgical risk.

[figure not shown]
The FlexNav™ delivery system is indicated for transcatheter delivery of the Portico™ valve. The delivery system is indicated for insertion into the vessel with or without an arterial introducer sheath.

The FlexNav™ loading system is indicated for loading the Portico™ valve in the FlexNav™ delivery system.

#### 1.2 Study Design and Objectives

The primary objective of the PORTICO pivotal IDE FlexNav study (“FlexNav study”) is to characterize the safety of the second-generation FlexNav™ Delivery System (“FlexNav™ Delivery System”).

The FlexNav study will be conducted as a prospective, multicenter, investigational study arm of the PORTICO pivotal IDE trial. Up to 200 patients (includes a maximum of 100 roll-ins) with symptomatic, severe aortic stenosis considered by a local Heart Team to be high or extreme risk for surgical aortic valve implantation will be enrolled from up to 70 US and Australian IDE sites. Upon provision of informed consent, subjects will undergo Portico valve implantation via a transfemoral or alternative access approach. Subject selection and key data collection will follow the pivotal IDE protocol to facilitate direct comparison of safety outcomes with the randomized cohort.

#### 1.3 Study Endpoints

##### 1.3.1 Primary Endpoint

The primary safety endpoint of the FlexNav study is VARC II defined major vascular complications at 30 days.

### 1.3.2 Descriptive Endpoints

A selection of endpoints from the pivotal IDE trial including valve performance parameters, clinical function assessments and adverse events defined according to VARC II criteria will be assessed at 30 days and included in the PMA application:

#### Descriptive Endpoints:

1. Non-hierarchical composite of all-cause mortality, disabling stroke, life threatening bleeding requiring blood transfusion, acute kidney injury requiring dialysis, or major vascular complications at 30 days from the index procedure
2. All-cause mortality at 30 days from the index procedure
3. Disabling stroke at 30 days from the index procedure
4. Non-disabling stroke at 30 days from the index procedure
5. Life threatening bleeding requiring blood transfusion at 30 days from the index procedure
6. Major bleeding at 30 days from the index procedure
7. Acute kidney injury at 30 days from the index procedure
8. Minor vascular complication rates at 30 days from the index procedure
9. Permanent pacemaker insertion at 30 days from the index procedure
10. Paravalvular Leak (PVL) at 30 days from the index procedure
11. NYHA functional classification at 30 days from the index procedure
12. KCCQ Quality of Life (QOL) score from baseline to 30 days from the index procedure
13. Technical device success defined as successful vascular access, delivery and deployment of the Portico Valve; retrieval with the delivery system and correct positioning of a single valve in the proper anatomical location

Additional endpoints to be assessed at one year but not included in the PMA application:

1. Composite of all-cause mortality or disabling stroke at one year from the index procedure
  2. All-cause mortality at one year from the index procedure
  3. Disabling stroke at one year from the index procedure
  4. Non-disabling stroke at one year from the index procedure
  5. Paravalvular Leak (PVL) at one year from the index procedure
  6. KCCQ Quality of Life (QOL) score from baseline and one year from the index procedure
  7. NYHA functional classification at one year from the index procedure
- 

## 2. CLINICAL PROTOCOL

### 2.1 Background Information

In 2017, the AHA/ACC revised their guidelines in a focused update to make TAVR a class I indication (previously a class IIa indication) for the treatment of aortic valve stenosis in patients at prohibitive or high-surgical risk. As the use of TAVR expands into younger, lower risk populations, minimizing vascular complications which are amongst the most frequent and serious complications of TAVR is of paramount importance as studies show vascular and bleeding complications during the procedure are associated with increased morbidity and mortality risk.

Edwards LifeSciences and Medtronic are the current TAVR market leaders accounting for 95% of the global TAVI market share. Two key design elements of the commercially-available balloon-expandable Edwards Sapien 3 valve and self-expanding Medtronic CoreValve Evolut R/Pro valve systems that help mitigate the frequency of vascular and bleeding complications are: 1) a low insertion profile due to the use of a custom expandable sheath (Sapien 3) and integrated sheath (Evolut R/Pro); and 2) the ability to achieve precise valve placement without repositioning or with minimal need to re-sheath and reposition.

The safety and effectiveness of the Abbott (legacy St. Jude Medical) family of CE Marked Portico™ Transcatheter Aortic Heart Valves (size range 23-29mm) is currently being assessed in the PORTICO pivotal US IDE trial.

[REDACTED]

[REDACTED]

[REDACTED]

[REDACTED]

[REDACTED]

[REDACTED]

[REDACTED]

[REDACTED]

### 3.3 Instructions for Use

For instructions for use (IFU) of the Portico™ Transcatheter Aortic Heart Valve and FlexNav™ Delivery System please refer to the IFU (Number 600014467) which includes the following:

- Portico™ Transcatheter Aortic Valve (PRT-23-IDE, PRT-25-IDE, PRT-27-IDE, PRT-29-IDE)
- FlexNav™ Delivery System (FN-DS-SM-IDE, FN-DS-LG-IDE)
- FlexNav™ Loading System (FN-LS-SM-IDE, FN-LS-LG-IDE)

[REDACTED]

[REDACTED]

[REDACTED]

[REDACTED]

[REDACTED]

#### 4. RISK AND BENEFITS OF THE STUDY DEVICE AND CLINICAL STUDY

There are no changes to the risk or benefits reported in the pivotal IDE trial for subjects participating in the FlexNav Study. Please refer to the Portico™ Transcatheter Aortic Heart Valve and FlexNav Delivery System IFU for a description of risk to benefits and a list of the potential adverse events.

#### 5. STUDY POPULATION

##### 5.1 Study Cohort

The FlexNav study is limited to subjects with symptomatic, severe aortic stenosis who are determined to be at high or extreme operative risk for surgical aortic valve replacement. The operative risk determination will be based on the Society of Thoracic Surgeons (STS) Adult Cardiac Surgery Risk Calculator. A surgeon's assessment of operative comorbidities, including medical and anatomic factors not captured by the STS risk calculator will also be considered in determining a subject's operative risk.

[REDACTED]

##### 5.2 Inclusion/Exclusion Criteria

The inclusion/exclusion criteria for the FlexNav Study is the same as the pivotal IDE trial. Refer to Sections 5.1 and 5.2 of the main protocol for details.

Additional exclusion criteria for subjects being considered for Portico valve implantation via an alternative access approach using the FlexNav™ Delivery System include:

For transaortic access using the FlexNav™ Delivery System:

1. Subject has a distance between the annular plane and the aortic access site <7 cm (2.8")
2. Subject has a distance between the annular plane and the separate introducer sheath distal tip <6 cm (2.4")

For subclavian/axillary access using the FlexNav™ Delivery System:

[REDACTED]

[REDACTED]

1. Subject's access vessel (subclavian/axillary) has a distance between the annular plane and the integrated sheath distal tip <17 cm (6.7")
2. Subject's access vessel requires the delivery system to be advanced through a separate introduce sheath

### 5.3 Screening Process

Subject case reviews will be conducted to determine a patient's eligibility to receive a Portico valve (roll-in and analysis population) by the same independent Subject Selection Committee used in the pivotal IDE trial.

The risk definitions will be the same as the pivotal IDE trial to ensure a consistent patient population is enrolled. The Subject Selection Committee will provide final determination of a subject's risk classification and primary access approach. If a site disagrees with the Subject Selection Committee's final decision regarding risk classification and/or primary access approach the subject will not be eligible for enrollment in the study.

## 6. SUBJECT ASSIGNMENTS

Subjects in the FlexNav study are not randomized. All subjects will undergo a Portico valve implant attempt.

Subject assignments (roll-in or analysis population) will be assigned by the Sponsor after Subject Selection Committee approval and prior to enrollment, based on the primary implanting physician's recent Portico experience.

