### 6.4 Roll-in Registry

Prior to enrolling subjects in the pivotal IDE randomized cohort, sites will be required to complete a minimum of two (2) and up to three (3) roll-in patients per primary implanting physician. However, implanting physicians with prior Portico experience and with a minimum of 3 implants in the last 6 months will not be required to include roll-in patients.

For subjects enrolled under protocol version L or later, all primary implanting physicians irrespective of prior Portico implant experience will be required to complete a minimum of one (1) and up to three (3) roll-in patients using the FlexNav™ Delivery System.

All roll-in subjects will be added to the IDE Roll-in Registry. The roll-in subjects must meet all the inclusion criteria and none of the exclusion criteria and be approved by the Subject Selection Committee. These subjects will be followed per protocol for the duration of the study, or until subject's withdrawal or death. The roll-in subjects' data will not be included in the randomized population nor the primary data analysis; however, the data will be analyzed and presented separately.

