### **6.5 FlexNav Study**

High and extreme risk subjects with an annular size between 19-27mm with suitable anatomy for transfemoral or alternative access valve implantation using the FlexNav™ Delivery System (minimum vessel requirement  $\geq 5\text{mm}$ ) will be enrolled in the FlexNav study. All FlexNav study subjects will receive a Portico device (no randomization).

The number of roll-in patients required by a site before they can contribute to the FlexNav study will be at the discretion of the Sponsor. All roll-in subjects will be designated as such prior to enrollment and will be added to the IDE Roll-in Registry.

Following the successful completion of roll-in subjects, sites will enroll subjects into the FlexNav study. These enrolled subjects will be considered part of the 'analysis population'.

Analysis subject data (excluding roll-ins) will be summarized and presented separately to the randomized cohort in the PMA application.

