### 6.1 Subject Enrollment

Subjects will be considered enrolled into the FlexNav study after completion of all of the following steps:

1. Signed informed consent is obtained.
2. Based on the screening assessments, it is determined that the subject meets all of the inclusion and none of the exclusion criteria.
3. Subject is approved by the Subject Selection Committee.
4. Subject assignment (roll-in or analysis) has been determined by the Sponsor.
5. The Portico delivery system enters the subjects' body.

Subjects who are approved by the Subject Selection Committee to receive a Portico valve via transfemoral access and are found during the procedure not to be suitable for this delivery modality (per the heart team medical decision) may receive a Portico valve using an alternate access modality and vice versa. This will be considered a protocol deviation unless the Subject Selection Committee pre-approved the subject for multiple access sites. The rationale for this decision must be documented by the site.

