## 6.2 Roll-in Cohort

A minimum of one (1) and up to three (3) roll-in subjects will be required per primary implanting physician at each site. Data from roll-in subjects will be added to the IDE Roll-in Registry and will not be included in the analysis population of 100 subjects. A maximum of 100 roll-in subjects will be permitted in the study.

The total number of roll-in subjects required per site will be at the discretion of the Sponsor and will be based on the primary implanting physician's recent Portico implant experience.

[REDACTED]

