1.6 Blinding

Subjects were not blinded to their assigned treatment. Packaging and design of the Portico and CAVs are different, and thus, implanters were not blinded to the assigned treatment. There was no randomization or blinding of treatment in the FlexNav cohort.

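### Does labelling FlexNav subjects as roll-in or analysis only after committee approval let the sponsor choose which cases count?

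*Protocol*

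**What the plan says.** Appendix W of the Protocol, section 6, states that roll-in or analysis status "will be assigned by the Sponsor after Subject Selection Committee approval and prior to enrollment, based on the primary implanting physician's recent Portico experience". Section 6.1 of the appendix gives the same order as numbered steps. Committee approval is step 3. Step 4 reads "Subject assignment (roll-in or analysis) has been determined by the Sponsor". Step 5, entry of the delivery system into the body, completes enrollment.

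Section 6.2 of the appendix requires one to three roll-ins per primary implanting physician. It keeps them out of the analysis population of 100, caps them at 100, and says that the total per site "will be at the discretion of the Sponsor and will be based on the primary implanting physician's recent Portico implant experience". Text directly after this is redacted.

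The main Protocol agrees. Section 6.4 says of every lead implanter, from version L onward: "irrespective of prior Portico implant experience will be required to complete a minimum of one (1) and up to three (3) roll-in patients". These cases are done with the FlexNav system. Section 6.5 says the number of roll-ins "required by a site before they can contribute to the FlexNav study will be at the discretion of the Sponsor", that roll-ins are designated before enrollment, and that sites move on to FlexNav analysis subjects once the roll-ins are done. Section 6.4 adds that for roll-ins "the data will be analyzed and presented separately".

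Eligibility is reviewed "by the same independent Subject Selection Committee used in the pivotal IDE trial" (Appendix W, section 5.3). The SAP, section 1.6, confirms: "There was no randomization or blinding of treatment in the FlexNav cohort".

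**The concern.** Three features together invite suspicion. The study has one arm and is open. The party that labels each subject is the sponsor, whose premarket application the result supports. And the label comes after the committee has fixed the patient's risk class and access route, although the stated basis, the physician's recent experience, has nothing to do with the patient. A reader may ask why the label should wait for patient information that it is not supposed to use.

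At stake is FlexNav's primary endpoint, major vascular complications at 30 days. If patients with difficult vessels were labelled roll-in and easier ones analysis, the rate in the 100 counted subjects would come out too low. The descriptive comparison with the first-generation delivery system in the randomized Portico arm (Appendix W, section 10.3; SAP 2.3.2) would then flatter the new system.

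**Working it through.** **1. What is timed.** Two decisions need to be kept apart: how many roll-ins an implanter must do (one, two or three), and which label a given subject carries. Appendix W, sections 6 and 6.1, place the second between committee approval and device entry. They do not say when the first is made. Section 6.5 of the main Protocol describes the number as something a site must complete before it can contribute, which reads as a requirement set in advance. No visible passage lets the sponsor change it once a case has been approved.

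**2. Why a label naturally comes late.** Once the number is set, the label follows from the implanter's running count. That count moves only when a device enters a patient, because that is the point of enrollment. An approved patient who is never attempted does not use up a slot. The number can be fixed early, but a subject's label cannot be final until the order of procedures is known. Labelling after approval is therefore what a sequential roll-in rule requires in practice.

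**3. What is left to discretion.**
- An implanter's first case is always a roll-in (main Protocol 6.4; Appendix W 6.2).
- Roll-ins precede analysis subjects (main Protocol 6.5), so a later difficult case cannot be pulled out once counting has begun.
- Status is set before device entry, so it cannot follow the subject's own outcome.
- An independent Clinical Events Committee adjudicates the endpoint (Appendix W, section 9.1).

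Only the second and third cases of an implanter are open, and the stated criterion for them is experience.

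**4. The plan's own figures.** Up to 200 patients with at most 100 roll-ins (Appendix W 1.2) gives 200 − 100 = 100, the stated analysis population. With one implanter at each of up to 70 sites (an assumption), one to three roll-ins each would make 70 to 210 against a cap of 100. That leaves 100 − 70 = 30 slots beyond the compulsory first, or 100/70 = 1.43 roll-ins per implanter. The choice among one, two and three is real but limited.

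**5. Size if the criterion were ignored.** The visible text gives no event rate, share of difficult cases or number of cases per implanter, so all of these are assumed. Let a share s = 25% of cases be difficult with risk r = 20%, and let the overall risk be 10%. The risk in the other cases is (0.10 − s·r)/(1 − s) = (0.10 − 0.05)/0.75 = 6.67%. Suppose the sponsor keeps case 2, and then case 3, as roll-in only when it is difficult. Counting starts at case 2 with probability 1 − s = 0.75, at case 3 with s(1 − s) = 0.1875, and at case 4 with s² = 0.0625. A start at case 2 or 3 is an easy case, and every later case carries 10%.

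For four cases per implanter:
- expected events = 0.75 × (0.0667 + 0.20) + 0.1875 × (0.0667 + 0.10) + 0.0625 × 0.10 = 0.2375
- expected counted cases = 0.75 × 3 + 0.1875 × 2 + 0.0625 × 1 = 2.6875
- apparent rate = 0.2375/2.6875 = 8.8%

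| Cases per implanter | Apparent rate when the truth is 10% |
|---|---|
| 3 | 8.1% |
| 4 | 8.8% |
| 6 | 9.3% |
| 8 | 9.5% |

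At four cases, with s from 10% to 40% and r from 15% to 30% (feasible pairs only), the range is 6.6% to 9.8%. The 6.6% requires every other case to carry no risk at all. For comparison, 10 events in 100 has an exact 95% interval of 4.9% to 17.6%.

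**The case for a change.** The strongest case for the concern is about demonstrability. The label follows the arrival of patient information that it does not need, and the sponsor has discretion over the number. No threshold linking experience to one, two or three is visible. For the randomized cohort, by contrast, section 6.4 of the Protocol states an explicit exemption based on at least 3 implants in the last 6 months. Labelling before enrollment rules out selection on the subject's own outcome, but not on features known at approval. Dating each implanter's number before cases are submitted, and adding a row for all attempts combined, would cost little.

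Parts of this stand. The order of steps is as described, the discretion exists, and a dated record would be good practice. The rest does not make an error of the plan:

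- The text after Appendix W 6.2 is redacted, as are the content of 6.3 on proctoring and that of section 11.10 of the main Protocol on FlexNav and registry methods. A rule or a date may stand there, and its absence from the public text is no gap in the plan. For the same reason one cannot say that the sponsor's records would fail to show independence.
- Filling slots in order of implant attempt, which any remedy would need, itself means that labels cannot be settled before approval.
- A combined row would mix in the learning-curve cases that the design sets aside on purpose. Because roll-in data are presented separately, a reader can add the two groups. At a common assumed rate of 10% and the maximum of 100 roll-ins, 20 events in 200 has an exact 95% interval of 6.2% to 15.0%. No conclusion of the study depends on that row.

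**Conclusion.** The concern does not hold. Followed as written, the plan ties roll-in status to the implanter's experience alone, fixes it before the procedure, and puts roll-ins ahead of counted subjects. Bias would need the sponsor to depart from its own criterion, use case details that no passage says it consults, predict difficulty correctly, and do so across implanters. The documents show no sign of this.

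Even then, the assumed scenario moves a true 10% to between 8.1% and 9.5% for three to eight cases per implanter. The extreme of 6.6% also lies within the exact interval of 4.9% to 17.6% at n = 100. These sizes rest on assumed rates and shares and illustrate scale only. FlexNav's comparison with the first-generation system is descriptive, and the randomized primary analyses do not use these subjects. What remains is a preference about documentation, on a point that the redacted text may already cover.
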